7 LABORATORY MEASURES

MELD (Model for End Stage Liver Disease) labs will be summarized as mean (SD), median (25, 75 percentiles), min and max by visit for the baseline visit, and 3, 6, 9, 12 month visits.

8 MEDICATIONS RELATED ANALYSIS

8.1 Concomitant Medications

Specific medication types prescribed as a result of the intervention through 3 months will be summarized as counts (percentages) for the patients in the ITT and mITT population. Medication types include medications for pain (opioids, OTC analgesics, herbal supplements), depression/anxiety, anti-psychotic, insomnia medications, itching medications, diuretics, beta-blockers, and Rifaximin.

9 ADDITIONAL NON-ENDPOINT ASSESSMENTS

Three additional assessments will be summarized. ECOG (Eastern Cooperative Oncology Group) will be summarized as counts (percentages) by visit for the initial, 1, 2, 3-month visits. The individual components that make up the CTP (Child-Turcotte Pugh Score) and the CTP class will be summarized as counts (percentages) and the CTP score will be summarized as mean (SD), median (25, 75 percentiles), min and max for the baseline, 3, 6, 9,12 month visits. The individual components of the AUDIT (Alcohol Use Disorders Identification Test) will be summarized as counts (percentages) and the AUDIT partial and total scores will be summarized as mean (SD), median (25, 75 percentiles), min and max for the baseline and 3 month visit.

10 DATA SOURCES

SAS datasets created from the PAL-LIVER eCRF (Electronic Case Report Form) contains data entered by participating sites, as well as data entered by patients and caregivers.

11 TIMING OF ANALYSES

11.1 DSMB Analyses

DSMB (Data and Safety Monitoring board) will have planned reviews of data approximately every 6 months starting after enrollment through the end of trial follow-up. Unscheduled data review meetings may be called by the DSMB or held at the request of the EC (Executive Committee).

11.2 Final Analyses

The final analyses will be carried out after the last enrolled patient has completed the 6th month follow-up assessment, the database has been cleaned and database lock has occurred. A preliminary analysis of the primary endpoint will take place after the month 3 visit data has been entered and substantially cleaned. Data will be exported from the clinical database and archived for the month 3 analyses.

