3.5.2 Secondary Efficacy Endpoints

The endpoints inset below will be assessed as a change from baseline to 3 months (3-month score minus baseline score) in the mITT population:

- Overall quality of life (PROMIS-29, separate T scores)
- Symptom burden (modified ESAS, point score for each item, potentially total score for ESAS-r (9 components) and total score for the 13 components from this study)
- Depression severity (PHQ-9, total score)
- Distress (Distress Thermometer, total score)
- Satisfaction with care (FAMCARE-P, total score)
- Caregiver burden (ZBI-12, total score)
- Caregiver quality of life (PROMIS-29, separate T scores)
- Goal concordant care (Patient and Caregiver Questionnaire, total score)

Healthcare utilization in the mITT population:

- Proportion of patients with at least one scheduled or unscheduled hospital admissions within 30 days from the initial visit (based on data available from 1 month visit).
- Proportion of patients with at least one scheduled or unscheduled hospital admissions within 90 days from the initial visit (based on data available from 3 months visit).
- Rate of ER visits within 1 year from the initial visit.
- Rate of unscheduled office visits within 1 year from the initial visit.

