3.5.3 Exploratory Endpoint

Survival over 1 year in the ITT population. We will use the date of informed consent as the first day in the trial. Or those alive, follow-up time will be censored at the time of loss to follow-up or at the time of completion of the study.

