3 PATIENT DISPOSITION

Patient disposition will be summarized for the ITT population with counts and percentages for all patients and will include the following:

- Patient who completed study (enrollment to 1 year follow-up).
- Evaluable patients (patients for whom FACT-Hep baseline to 3 months change score can be calculated).
- Patients who underwent liver transplantation or hospice transfer prior to the 3 month end point assessment.
- Patients who discontinued the study and reasons for study discontinuation.

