5.4 Secondary Efficacy Analyses

The secondary endpoints will be presented as descriptive statistics by visit.

Where appropriate (i.e., change from baseline can be calculated), models similar to the primary endpoint superiority analysis may be utilized for secondary endpoint analyses.

The healthcare utilization endpoints will be analyzed as follows. For scheduled and unscheduled hospital admissions within 30 and 90 days of enrollment, proportions will be analyzed using random effects logistic regression. Counts of hospital admissions, ER visits, and unscheduled office visits over 1 year will be analyzed using Poisson regression with robust standard errors and non-identity dispersion via generalized estimating equations.

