5.5 Exploratory Analyses

Survival will be summarized with Kaplan-Meier curves. Cox regression will be used for multivariable models, and robust standard errors will be used to account for within center clustering. ITT population will be used for the survival analyses.

Longitudinal analysis of FACT-Hep total score at 1, 2, 3, 6, 9 and 12 months will be performed utilizing the ITT population. Measurements of Fact-Hep will be set to missing after patients receive liver transplant or are transferred to hospice. A mixed model will be considered with center as a random effect and unstructured covariance structure (alternatively autoregressive covariance structure in case of a convergence difficulty) for repeated measurements of FACT-Hep over time within a patient. As in the primary analysis, the model will have treatment effect and adjustment for baseline FACT-Hep total score and VA status.

Additional covariates will be considered for multivariable modelling. MI will be utilized if more than 10% of missing records are present.

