12.4 Handling of Missing Data

Every effort will be made to minimize the extent of missing values by proactive strategies, inevitably we will need to deal with some missing value problems [3]. To prevent and limit

missing data other than due to patient's death or curative therapy prior to completion of the study we will perform data checks and consistency checks during the study and collaborate with sites to complete missing or incorrect data items. If \leq up to 10% of patients have missing data for a particular analysis, we will conduct complete case analysis utilizing only non-missing data. However, if more missing data ($> 10\%$) is present we will utilize multiple imputations (MI) to mitigate potential bias of the complete case analysis and appropriately reflect the uncertainty due to imputations [4]. The MI method assumes that the data are missing at random (MAR), meaning that the probability of missingness depends on observed data but not on unobserved data. An imputation model will be constructed including all variables that are part of the analysis model and additional auxiliary variables (including age, gender, education level, employment status, marital status, and smoking status) that may be predictive of the missingness. Both continuous and categorical variables will be included. Multiple imputation will be performed using the PROC MI procedure in SAS 9.4 utilizing fully conditional specification (FCS) method for data sets with arbitrary missing patterns [5]. A total of 1000 imputations will be performed. Each of the imputed datasets will be analyzed separately, and the results will be combined using SAS PROC MIANALYZE to obtain valid statistical inferences that reflect the uncertainty due to imputations of missing data and account for the variability both within and between the imputed datasets.

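### The final analyses are tied to the last patient's month 6 with no later data cut, although several outcomes run to 12 months; the 1-year count models state no time at risk, and the 30/90-day admission window has two origins.

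*SAP*

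**What the plan says.** **Timing.** SAP 11.2 names two analysis times. One is a preliminary month-3 analysis of the primary endpoint. For the other, "The final analyses will be carried out after the last enrolled patient has completed the 6th month follow-up assessment", with cleaning and lock to follow. No later lock or cut-off date appears in the SAP or the protocol.

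**Outcomes that pass month 6.** SAP 3.5.2 lists "Rate of ER visits within 1 year from the initial visit" and the matching rate for unscheduled office visits. SAP 3.5.3 has survival over 1 year, where for patients still alive "follow-up time will be censored at the time of loss to follow-up or at the time of completion of the study". SAP section 3 counts a patient as having completed the study at 1 year of follow-up. In SAP 5.5, "Longitudinal analysis of FACT-Hep total score at 1, 2, 3, 6, 9 and 12 months will be performed".

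**Count model.** SAP 5.4 says: "Counts of hospital admissions, ER visits, and unscheduled office visits over 1 year will be analyzed using Poisson regression with robust standard errors". It mentions no offset, exposure or end of risk. The 1-year admission count in that sentence is not among the endpoints in SAP 3.5.2.

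**Missing data.** Under SAP 12.4, if up to 10% of patients "have missing data for a particular analysis, we will conduct complete case analysis utilizing only non-missing data"; above 10%, multiple imputation is used. It does not say whether a shortened count is missing.

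**Admission windows.** SAP 5.4: "For scheduled and unscheduled hospital admissions within 30 and 90 days of enrollment, proportions will be analyzed". SAP 3.5.2 and protocol 5.3 start both windows at the initial visit. SAP 3.5.2 adds that the 30-day endpoint rests on 1-month visit data and the 90-day endpoint on 3-month visit data.

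**The concern.** Three gaps meet in the same set of outcomes.

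1. Taken literally, SAP 11.2 allows the database to be locked before the latest entrants have been followed for 9 or 12 months. The SAP does not say that this would be an administrative cut, or on what date.
2. A count collected over less than a year has no stated treatment. It could be entered as if it covered the year, dropped, or imputed. The first choice understates the rate.
3. The analysis section and the endpoint section define different 30/90-day windows. The stated data source can also close before the window does, so a late admission could be missed.

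The ER-visit, office-visit and 30/90-day admission outcomes carry directional hypotheses in protocol 5.3. Two statisticians following the SAP could report different values for them from the same data. The 3-month primary endpoint and the 3-month score outcomes are not touched.

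**Working it through.** The plan states no figure for this point, so there is none to reproduce. The steps below illustrate size only.

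**Inputs from the documents**
- 936 patients (SAP section 2).
- Enrollment in years 2 through 7 (protocol 5.2), which is 6 years or 72 months.
- Initial visit up to 6 weeks (42 days) after consent (SAP section 2).
- 1 month = 30 days; visits at months 1 to 3 may fall 1 week either side (protocol Table 2).
- One-year survival of about 80% for most complications (protocol 5.5).

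**Assumptions.** Even accrual by date of initial visit, since the accrual curve is not given. The lock falls L months after the last month-6 assessment, since the lock date is not given.

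**Step 1. Follow-up cut short by the lock**
- Share without month 12 = (6 − L)/72.
- Share without month 9 = max(0, 3 − L)/72.
- Those cut short lack (6 − L)/2 months on average, so 1-year person-time lost = share without month 12 × (6 − L)/24.

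| L (months) | Without month 12 | Without month 9 | Person-time lost |
|---|---|---|---|
| 0 | 6/72 = 8.3% (78) | 3/72 = 4.2% (39) | 0.0833 × 6/24 = 2.1% |
| 3 | 3/72 = 4.2% (39) | 0 | 0.0417 × 3/24 = 0.5% |
| 6 | 0 | 0 | 0 |

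The result scales with the accrual rate in the final 6 months. At L = 0, half the average rate gives 0.5 × 78 = 39 patients and 1.0% of person-time. One and a half times the average gives 1.5 × 78 = 117 patients (12.5%) and 3.1%.

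**Step 2. Time at risk shortened by death, whatever the lock date.** Under an assumed constant hazard, mean observed time in the year is (1 − S)/(−ln S), where S is one-year survival. For S = 0.80 this is 0.20/0.2231 = 0.896 year. For S = 0.75 and 0.85 it is 0.869 and 0.923. The trial's own survival may differ. An exposure term is therefore needed even if every survivor reaches month 12.

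**Step 3. Two window origins.** The SAP does not define enrollment. Assume that it means consent, and let g be the days from consent to the initial visit. The two 30-day windows share max(0, 30 − g) days and the two 90-day windows share 90 − g.
- g = 0: 30 and 90 days.
- g = 14: 16 and 76 days.
- g = 42: 0 and 48 days.

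**Step 4. Visit data that precede the end of the window.** The earliest 1-month visit is day 30 − 7 = 23, leaving 7/30 = 23% of the window uncovered. The earliest 3-month visit is day 90 − 7 = 83, leaving 7/90 = 8%. A visit on or after day 30 or day 90 leaves nothing uncovered.

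**The case against.** **The lock may be late enough.** SAP 11.2 gives an earliest trigger, and cleaning and lock follow it. Protocol 5.2 ends enrollment in year 7 and assigns year 8 to analysis. A lock 6 months after the last month-6 assessment would lose nothing. This stands: lost follow-up is possible but not established. What remains is that no rule requires a later lock and no date is given.

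**Survival already copes.** Kaplan-Meier and Cox methods accept administrative censoring, and the censoring text in SAP 3.5.3 can be read that way. This also stands. Only the date is missing, together with a reading of completion that does not clash with SAP section 3.

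**A Poisson model for a rate conventionally has an offset.** SAP 3.5.2 does call two of these outcomes rates, so taken alone the missing offset is close to missing detail. It matters more because SAP 5.4 speaks of counts over 1 year while SAP 11.2 permits an early lock.

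**Enrollment is one slip.** The initial visit is used everywhere else, so the intent is fairly clear. But the slip sits in the analysis section, where a programmer would look.

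**Stronger readings a reader might infer, which the documents do not support**
- *The arm comparison is biased.* Four of the five later-added sites are hepatologist-led (protocol 5.2), so later entry in that arm is plausible. Accrual by arm is not given, and neither direction nor size can be established.
- *The 8.3% is a ceiling.* Even accrual is not a worst case. Sites were added in year 3 to raise enrollment, which could load the tail. Protocol 11.2 expects only a few more evaluable patients, but that concerns the 3-month endpoint at one date.
- *Enrollment was much shorter, so the loss is larger.* Protocol section 10 still describes enrollment in years 2 to 4. That conflicts with protocol 5.2 and looks like leftover text.
- *Truncation decides which side of the 10% rule in SAP 12.4 applies.* These outcomes use the mITT population, whose size is not given, and deaths could pass the limit alone if they count as missing.

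**Conclusion.** The point holds as a set of inconsistencies in the rules for the 12-month outcomes and the admission windows. Followed literally, the SAP allows truncated 1-year counts to be modelled as full-year counts, 30/90-day windows to start from an origin that contradicts the endpoint definition, and admissions in the last days of a window to be missed.

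The illustrative effect of the data cut is modest: 8.3% of patients and 2.1% of person-time, if accrual was even over 72 months and the lock fell at the last month-6 assessment, and nothing with a lock 6 months later. The origin conflict needs no accrual assumption, though its size depends on enrollment meaning consent and on the actual gap to the initial visit. The visit-timing gap arises only for visits held before day 30 or day 90.

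The 1-year secondary rates, the admission outcomes and the exploratory analyses to month 12 are affected. The primary endpoint is not. Correction is worthwhile before the final lock, with moderate confidence in how much it would change results.

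**What to change.** 1. **SAP 11.2 and 3.5.3.** Keep the month-3 analysis of the primary endpoint. Then either analyse the 1-year outcomes after the last patient's month 12, or name a data-cut date and use it in SAP 3.5.3 for administrative censoring.
2. **SAP 5.4, counts.** Add log time at risk as an offset, running from the initial visit to the earliest of death, withdrawal, loss to follow-up, data cut or day 365. The model then matches the rate endpoints. Report person-time and deaths by arm. Say how patients without an initial visit are handled, since their time at risk is undefined. Other ways of treating death are defensible, but one must be stated.
3. **SAP 5.4 and 3.5.2, admissions.** In SAP 5.4, replace enrollment with the initial visit as the origin. In SAP 3.5.2, classify admissions by admission date, using utilization data from all later visits.

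**Cost.** Mostly SAP wording and some programming. Utilization is already collected at each study visit from medical records and patient history (protocol Table 2 and section 9). The documents do not show whether admission dates are in the eCRF. If not, they must be retrieved from the medical record, which could be real work across 19 sites. The month-12 option may delay the lock, but for the 1-year outcomes only.

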12 STATISTICAL CONSIDERATIONS

12.1 General Analysis Conventions/Rules

Continuous variables will be summarized as number of observations, mean, standard deviation (SD), minimum, 25th percentile, median, 75th percentile, and maximum. Categorical variables will be summarized as frequency counts and percentages. Statistical comparisons will be performed using two-sided significance tests.

12.2 Statistical Software

The majority of the statistical analyses will be performed using SAS[®], version 9.4 or higher (SAS Institute Inc., Cary, NC) and R statistical software. Additional statistical software will be utilized as needed.

12.3 Verification of Programming Codes

All tables, listings, and graphs will be verified and reviewed before being considered final. The verification process will ensure that the numbers are produced by a statistically valid method and that the execution of the computations is correct. Suitably qualified personnel who have not been previously involved in the production of the original programming code will perform the verification procedures. Methods of verification will include independent programming of all analysis datasets as specified in the DCRI Statistical Standard Operations Procedures (SOPs). Tables will be reviewed for accuracy, consistency with this analysis plan, consistency within tables, and consistency with corresponding output. Once verification is complete, all documentation of the verification process will be filed in the study statistical documentation repository for PAL-LIVER as required by the DCRI statistical SOPs of the Duke Clinical Research Institute (DCRI).

12.4 Handling of Missing Data

Every effort will be made to minimize the extent of missing values by proactive strategies, inevitably we will need to deal with some missing value problems [3]. To prevent and limit

missing data other than due to patient's death or curative therapy prior to completion of the study we will perform data checks and consistency checks during the study and collaborate with sites to complete missing or incorrect data items. If \leq up to 10% of patients have missing data for a particular analysis, we will conduct complete case analysis utilizing only non-missing data. However, if more missing data ($> 10\%$) is present we will utilize multiple imputations (MI) to mitigate potential bias of the complete case analysis and appropriately reflect the uncertainty due to imputations [4]. The MI method assumes that the data are missing at random (MAR), meaning that the probability of missingness depends on observed data but not on unobserved data. An imputation model will be constructed including all variables that are part of the analysis model and additional auxiliary variables (including age, gender, education level, employment status, marital status, and smoking status) that may be predictive of the missingness. Both continuous and categorical variables will be included. Multiple imputation will be performed using the PROC MI procedure in SAS 9.4 utilizing fully conditional specification (FCS) method for data sets with arbitrary missing patterns [5]. A total of 1000 imputations will be performed. Each of the imputed datasets will be analyzed separately, and the results will be combined using SAS PROC MIANALYZE to obtain valid statistical inferences that reflect the uncertainty due to imputations of missing data and account for the variability both within and between the imputed datasets.

12.5 Addressing not answered survey questions

In some cases, patients fail to answer all of the survey questions, leading to inaccurate calculated raw scores which consider only the answered questions. Some assessment surveys provide mechanisms for addressing partially answered questionnaires. For assessments, which do not provide explicit recommended mechanisms, we will use the following approach to adjust the raw score.

If at least 70% of the questions are answered, we will compute an adjusted score according to the following formula: $\text{adjusted score} = (\text{raw score}) * (\text{number of questions in a survey}) / (\text{number of questions answered})$. This is equivalent to imputing the average value of answered questions for the not answered questions.

If less than 70% of the questions are answered, the survey score will be set to missing.

12.6 Multiple Comparisons

We will not perform multiple comparison adjustment in this study.

## ABBREVIATIONS

ASCO	American Society of Clinical Oncology
AUDIT	Alcohol Use Disorders Identification Test
BCLC	Barcelona Clinic Liver Cancer
CRF	Case Report Form
CTP	Child-Turcotte Pugh Score
DCC	Data Coordinating Center
DCRI	Duke Clinical Research Institute
DSMB	Data Safety and Monitoring Board
EMR	Electronic Medical Record
ER	Emergency Room
ESAS	Edmonton Symptom Assessment Scale
ESLD	End Stage Liver Disease
EWB	Emotional well being
FACT-G	Functional Assessment of Cancer Therapy – General
FACT-Hep	Functional Assessment of Cancer Therapy – Hepatobiliary
FAMCARE-P	Family Satisfaction with Care-Patient
FWB	Functional well being
HCC	Hepatocellular Cancer
HCS	Hepatobiliary cancer subscale
HCV	Hepatitis C
HIPAA	Health Insurance Portability and Accountability Act
HTE	Heterogeneity of Treatment Effect
ICC	Intraclass correlation coefficient
IRB	Institutional Review Board
LT	Liver transplant
MCID	Minimally clinically important difference
MELD	Model for End Stage Liver Disease
MI	Multiple imputations
MRN	Medical record number
NASH	Non-Alcoholic Steatohepatitis
NCCN	National Comprehensive Cancer Network
OPTN	Organ Procurement and Transplantation Network
PC	Palliative Care
PHQ-9	Personal Health Questionnaire
PROMIS-29	Patient Reported Outcomes Measurement Information System
PWB	Physical well being
QOL	Quality of Life
RAB	Research Advisory Board
RCT	Randomized controlled trial
SBP	Spontaneous Bacterial Peritonitis

SD	Standard deviation
SES	Social economic status
SFWB	Social and family well being
VA	Veterans Affairs
ZBI-12	Zarit Burden Interview

